## 1.6 Secondary endpoints

The following secondary parameters will be assessed in this study:

1. PPV, NPV, LR+ and LR- of the AIVARIX tool in detecting C 1 class of CVD
2. PPV, NPV, LR+ and LR- of the AIVARIX tool in detecting C 2 class of CVD

Based on the same table as mentioned in the section 1.4, the following formulas will be used to calculate the parameters of interest:

Positive predictive value(PPV)=[ $a/(a+b)$ ] $\times 100$

*Negative predictive value(NPV)=* $[d/(c+d)] \times 100$ .

$$\text{Positive likelihood ratio (LR +)} = \frac{\text{Sensitivity}}{100 - \text{Specificity}}$$

$$\text{Negative likelihood ratio (LR -)} = \frac{100 - \text{Sensitivity}}{\text{Specificity}}$$

95% confidence intervals will be calculated using the normal approximation (Wald's) method for PPV, NPV, LR+ and LR- parameters.

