## Aim of the program

The main goal of this study is to describe the AIVARIX app accuracy in detecting C1 and C2 classes by CEAP classification of chronic venous disease (CVD) in patients who are consulted by phlebologists on symptoms and signs suggestive to CVD.

Primary goal(s):

The primary goal of the study is to estimate Sensitivity (Sn) and Specificity (Sp) of the AI-based AIVARIX app in detecting C1 and C2 classes of CVD in patients who are seeking for professional advice from a phlebologist regarding symptoms and signs suggestive to CVD.

- Sensitivity is defined as the ratio of the number of positive cases of detection of signs of C1 or C2 CVD, identified using the AIVARIX tool, to the total number of truly positive cases of C1 or C2 CVD in the study population, confirmed by phlebologists using objective / instrumental examinations.
- Specificity is defined as a proportion of the number of negative cases of signs C1 or C2 classes of CVD identified by the AIVARIX tool divided to overall truly negative cases of C1 or C2 in the study population confirmed by phlebologists by means of objective/ instrumental examination.

Once Sn and Sp of the application is estimated, positive and negative likelihood ratios (LR) will be calculated.

Secondary goal(s):

Secondary objectives are to calculate the positive and negative predictive values (PPV and NPV, respectively) of AIVARIX in detecting signs of C1 and C2 classes of chronic venous disease.

PPV is defined as the proportion of true positive cases of class C1 or C2 CVD detected using AIVARIX as a proportion of the number of true positive and false positive cases of class C 1 or C 2 identified using the AIVARIX application and confirmed by phlebologists.

The NPV is defined as the ratio of the number of true negative cases of C 1 or C 2 CVD detected using AIVARIX to the true negative and false negative cases of C 1 or C 2 CVD detected using AIVARIX and confirmed by phlebologists.

Primary Variables:

- Sensitivity and specificity of the AIVARIX app in detecting C 1 class of CVD.
- Sensitivity and specificity of the AIVARIX app in detecting C 2 class of CVD.

Secondary Variables

- PPV, NPV, LR+ and LR- of the AIVARIX app in detecting C 1 class of CVD
- PPV, NPV, LR+ and LR- of the AIVARIX app in detecting C 2 class of CVD

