## Methodology

This is a cross sectional multicenter prospective observational study. It will include patients seeking phlebologist's consultation with any signs and symptoms suggestive to CVD including but not limited to C1 and C2 classes as well as patients without CVD who have other skin pathologic conditions of lower extremities that require differential diagnosis with CVD. Twenty-one phlebologists consulting in outpatient clinics across the country will be participating in the study.

The total number of patients as well as the number of patients with CVD C1 and C2 classes, the number of patients with other classes of CVD and the number of patients with other skin pathologic conditions of lower extremities are estimated given data on prevalence of CVD classes in general population available for Russia and other countries. This estimation is described in the "Sample size calculation and justification" paragraph. According to the mentioned estimation a distribution of patients to be enrolled in the study by each participating phlebologist should be as following:

- 20 subjects overall of whom:
  - 6 patients with CVD C1 class
  - 4 patients with CVD C2 class;
  - 2 patients with CVD with classes other than C1-C2 (C4-C6);
  - 8 patients with either C0s CVD or with skin pathologic conditions of lower extremities other than CVD;

Patients will be screened by a phlebologist and if meet inclusion/ non-inclusion criteria and provide written consent to participate in the study will be included in the study. Phlebologist will evaluate patients' status locales in accordance to routine clinical practice to objectively confirm or exclude presence of CVD and to define a class of the disease if present. Presence of CVD and associated class by C will be confirmed based on results of diagnostic methods used in routine clinical practice (presumably with use of objective examination, anamnesis morbi and ultrasonography of veins of lower extremities and/ or by venography of lower extremities, if necessary).

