Once the clinical evaluation is made, investigating physician will take one photo of the locus with spider veins in patients present with C1 class, or with varicose veins for patients present with C2, or locus with either no signs of pathology or with pathologic condition of the skin of lower extremities other than CVD in accordance to the distribution split described herein above, and then will upload the picture to the cloud storage. Phlebologists participating in the study will also record results of the clinical evaluation for each enrolled patient in the eCRF with imputing the information on presence or absence of CVD with obligatory indication of class by C as well as presence or absence of other skin pathologic condition(s) of lower limbs that required consultation and differentiation by phlebologist. If a patient has CVD simultaneously present with signs of C1 and C2 as well as with other classes of CVD a phlebologist will have to decide which locus of pathology to picture in accordance to the given distribution of patients to be enrolled. In case a patient has no CVD but any other skin pathologic condition of lower extremities of different nature a phlebologist will take one photo of the locus with a corresponding pathologic sign(s) and then upload it to the cloud. In any cases investigating phlebologist will record information on presence or absence of CVD indicating its class or other pathologic condition in the eCRF.

Each uploaded photo must be deindividualized and should have a unique ID code assigned to each patient.

In order to fulfill minimum requirements for technical characteristics of smartphones/ pictures to be taken, following criteria are to be satisfied:

- Smartphone is to be manufactured in 2015 or later but not earlier.
- Area of the interest is to occupy not less than 30% of the picture. To fulfill this requirement a smartphone has to be positioned so that the distance from the skin area of interest to smartphone's camera is in range of 30-50 cm.
- Plain background (a picture is to be taken at the background of plain/ monochromic wall/ surface without any additional subjects in focus including additional parts of the body, furniture or people, etc.).
- Smartphone is to be positioned in parallel to the skin area of interest.

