## 1.5 Primary endpoints

The following primary parameters will be assessed in this study:

1. Sensitivity and specificity of the AIVARIX tool in detecting C 1 class of CVD.
2. Sensitivity and specificity of the AIVARIX tool in detecting C 2 class of CVD.

Calculation of all performance parameters will be based on the two-way table as follows (where “gold standard” stands for the current approach and “screening test” stands for AIVARIX-based approach; “positive” stands for signs

of C1 class of CVD or C2 class of CVD, “negative” stands for non-signs C1 class of CVD or non-C2 class of CVD, respectively):

Primary (operational) parameters of the AIVARIX method will be calculated as follows (presented as percentages):

$$Sensitivity = [a/(a+c)] \times 100$$

$$Specificity = [d/(b+d)] \times 100$$

95% exact binomial confidence intervals calculated using the Clopper-Pearson or Agresti-Coull method will be calculated for both sensitivity and specificity.

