## 1.11 Sample size calculation and justification

Sample size calculation for studies sensitivity and specificity is primarily based on two parameters: prevalence of true-positive cases in the population under study (disease prevalence) and acceptable sensitivity and specificity levels and precision of estimate.

According to the global data presented in the systematic review with pooled prevalence analysis of Salim S. et al., 2021 [1], pooled estimates for different CVD classes were: C0 s: 9%, C1: 26%, C2: 19%, C3: 8%, C4: 4%, C5: 1%, C6: 0.42%. Probably, the rest 32.58% corresponds for the absence of any sign of CVD.

According to the data for the Russian Federation presented by Zolotukhin I.A. et al., 2017 [2], about 30.8% of examined participants had no any sign of CVD; the prevalence of C0 were 5.4%, C1 – 34.3%, C2 – 21.3%, C3-6 – 8.2%. In the abstract of Cand. Sci. (Med.) Dissertation of Avakiants I.P., 2019 [3], the prevalence of C1 were estimated as 30.9%, of C2 – 19.3%.

So, we could estimate the summary prevalence for C 1 plus C 2 as approximately 50%, and the proportion “C2 : C1” as about 2 : 3.

Among the rest 50% of the population (without C 1 or C 2) we could roughly estimate the proportion of persons without any signs of CDV or with C0 class to the persons with C3-6 classes as 4 : 1.

Finally, persons without any signs of CDV or with C0 class could have some other (non-CVD) diagnosed and documented lower extremities skin conditions or they could be without any skin conditions of lower extremities at all. We do not estimate any proportions for this category.

With regards to the acceptable sensitivity and specificity, the estimates were based on the publication by Navarro T.P. Et al, 2002 [4], where targeted sensitivity is about 80% and higher while acceptable specificity should be 70% or above. Unacceptable level of both sensitivity and specificity is set to 60% based on the width of the 95% confidence intervals from the publication [4].

Accordingly, the following assumptions were made when calculating the sample size:

$$\begin{aligned} H_0: Se &= Se_0 \\ H_A: Se &\neq Se_0 \end{aligned}$$

$$\begin{aligned} H_0: Sp &= Sp_0 \\ H_A: Sp &\neq Sp_0 \end{aligned}$$

where

- $Se$  – target sensitivity
- $Se_0$  – null hypothesis (i.e. not acceptable) sensitivity
- $Sp$  – target specificity
- $Sp_0$  – null hypothesis (i.e. not acceptable) specificity

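### PPV and NPV in Section 1.6 come from a table whose C1 and C2 shares are set by enrolment quota, so they apply only at that mix, and the simple Wald intervals ignore that design

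*Combined protocol and SAP*

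**What the plan says.** The Aim of the program section makes PPV and NPV secondary objectives. It directs the study at accuracy "in patients who are consulted by phlebologists on symptoms and signs suggestive to CVD".

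The Methodology section says that the class numbers "are estimated given data on prevalence of CVD classes in general population available for Russia and other countries" and that "a distribution of patients to be enrolled in the study by each participating phlebologist should be as following": 6 C1, 4 C2, 2 of other CVD classes, and 8 with C0s or a non-CVD skin condition, per 20 patients. Where a patient shows several classes, "a phlebologist will have to decide which locus of pathology to picture in accordance to the given distribution of patients to be enrolled". Section 1.11 repeats the split as 124 C1 and 83 C2 among 414.

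Section 1.6 then sets PPV = a/(a+b) and NPV = d/(c+d): "Based on the same table as mentioned in the section 1.4, the following formulas will be used to calculate the parameters of interest". (The table is introduced in Section 1.5, not 1.4; that is only a cross-reference slip.) For PPV, NPV, LR+ and LR-, "95% confidence intervals will be calculated using the normal approximation" (Wald). Under Section 1.5, a negative "stands for non-signs C1 class of CVD or non-C2 class of CVD, respectively".

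The plan contains no conversion to another prevalence and no statement of the prevalence at which PPV and NPV apply.

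**The concern.** PPV and NPV depend on prevalence. Here the prevalence in the table is a design input: the quota fixes how many C1 and C2 images enter, down to the choice of lesion in patients with several classes. A reader who takes the reported PPV as the chance that a clinic patient flagged by the app has C1 or C2 would be using a quantity that the study does not estimate.

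Two further points follow from the same design.

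- A simple Wald interval treats a+b and c+d as fixed sample sizes. The quota instead approximately fixes a+c and b+d, so the standard error is that of a different sampling scheme.
- The negatives for C1 include C2 patients, and the negatives for C2 include C1 patients. Specificity, LR+ and LR- therefore carry the quota's comparator mix, and converting PPV and NPV to another prevalence does not remove that.

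**Working it through.** **Inputs.** From the Methodology section and Section 1.11: quota 6 C1 and 4 C2 per 20; 124 C1 and 83 C2 of 414; 372 analysed; sensitivity (Se) target 80% or higher, specificity (Sp) target 70% or higher. The first source in Section 1.11 reads "pooled estimates for different CVD classes were: C0 s: 9%, C1: 26%, C2: 19" per cent; the two Russian sources give C1 34.3% and 30.9%, C2 21.3% and 19.3%.

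**The plan's own figures.** 186/0.5 = 372, and 372/0.9 = 413.3, hence 414. The shares are 124/414 = 30.0% and 83/414 = 20.0%, which match 6/20 and 4/20. The 70% prevalence also listed in Section 1.11 is not the one behind 372 (186/0.3 = 620).

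**Dependence on the mix.** With prevalence p:

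- PPV = p·Se / [p·Se + (1-p)(1-Sp)]
- NPV = (1-p)·Sp / [(1-p)·Sp + p(1-Se)]

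For C1 at quota, PPV = 0.24/(0.24 + 0.21) = 53.3%. At Se 80%, Sp 70%:

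| Class | Prevalence | PPV | NPV |
|---|---|---|---|
| C1 | 30% (quota) | 53.3% | 89.1% |
| C1 | 26-34.3% (cited) | 48.4-58.2% | 90.9-87.0% |
| C1 | 20-50% (assumed for clinics) | 40.0-72.7% | 93.3-77.8% |
| C2 | 20% (quota) | 40.0% | 93.3% |
| C2 | 19-21.3% (cited) | 38.5-41.9% | 93.7-92.8% |
| C2 | 10-40% (assumed for clinics) | 22.9-64.0% | 96.9-84.0% |

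**Wald interval for PPV.** Take 372 analysed, with class totals n1/n0 of 111/261 (C1) and 74/298 (C2), and independent images. Write P for PPV.

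- Wald SE = √[P(1-P)/(a+b)]
- Fixed-total SD ≈ P(1-P)·√[(1-Se)/(n1·Se) + Sp/(n0(1-Sp))]

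For C1 at 80/70: a+b = 88.8 + 78.3 = 167.1 and P = 0.531. Wald SE = √(0.2490/167.1) = 0.0386. SD = 0.2490·√(0.00225 + 0.00894) = 0.0263. The ratio is 1.47. Enumerating both binomials exactly gives:

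| Se/Sp | Wald SE over true SD, C1 | C2 | PPV coverage, C1 | C2 |
|---|---|---|---|---|
| 80/70 | 1.46 | 1.57 | 99.5% | 99.8% |
| 90/70 | 1.51 | 1.66 | 99.7% | 99.9% |
| 80/60 | 1.61 | 1.72 | 99.8% | 99.9% |
| 90/90 | 1.16 | 1.23 | 97.2% | 98% |
| 80/98 | 1.01 | 1.02 | 89.8% | 93.1% |
| 80/99 | 0.94 | 0.96 | 92.5% | 89.2% |

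At 80/70 the mean half-width is 7.6 points against 5.2 needed (C1), and 7.9 against 5.0 (C2). With 414 analysed, C2 at 80/99 covers 85.2%. Under plain random sampling (414 analysed), Wald PPV coverage at 80/70 is 94.9% and 94.7%, so the excess width comes from the quota. A Wilson interval on a/(a+b) does not cure it (99.6% and 99.8%).

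**Wald interval for NPV.** At Se 95% with 372 analysed, coverage is 91.6% (C1) and 88.6% (C2); 18.6% and 47% of upper limits exceed 100%. With 414 analysed, C2 covers 92.1%. SE over SD is about 1, so the cause is skewness and discreteness rather than the quota.

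**Comparator mix.** At quota, the 14 non-C1 patients per 20 are 4 C2, 2 other classes and 8 C0s or non-CVD; the 16 non-C2 are 6 C1, 2 and 8. As an illustration, assume Sp 50% in the other early class, with Sp in the remainder set so that the total is 70% at quota (78% for C1, 82% for C2). Over the cited prevalences the converted PPV is then off by at most 0.9 points (C1) and 1.5 points (C2). At an assumed 42% C1 and 28% C2, Sp falls to 64.5% and 63.3%, and PPV is 62.0% instead of 65.9% (C1) and 45.9% instead of 50.9% (C2).

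**The case against.** Four arguments favour leaving Section 1.6 alone.

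- **The quota lies inside the cited prevalence ranges, and the mix is stated openly.** This stands: on documented figures the shift is modest. But those figures describe general populations, and the stated target is consulting patients.
- **The planned likelihood ratios let a reader convert.** They do, but Section 1.6 neither says so nor states the comparator mix they assume.
- **PPV and NPV are secondary, and no test or decision rule uses them.** This stands and limits the weight of the point.
- **The width result assumes independent images.** This also stands. Twenty-one phlebologists contribute about 20 patients each, take the photographs and choose the lesion, and Section 1.14 anticipates differences between sites. Inflate each variance term at 80/70 by 1 + (cluster size - 1)·ICC, with equal clusters. The ratio then falls from 1.47/1.58 (C1/C2, large-sample formula) at ICC 0 to 1.20/1.29 at 0.05, 1.04/1.12 at 0.10 and 0.93/1.00 at 0.15. These ICCs are assumptions; the documents give none.

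A reader might infer that the Wald PPV intervals are always too wide, hence conservative, and worst at the planning values. The documents' own targets do not support that. They are minimum values, so 90/70 lies within the planned range and has a larger excess than 80/70, while near Sp 98-99% the interval under-covers.

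**Conclusion.** The concern holds in a limited form. That PPV and NPV apply only at about 30% C1 and 20% C2 follows from the text and needs no assumption. The size of the gap for clinic patients cannot be known from the documents: the wide PPV ranges (40.0-72.7% for C1, 22.9-64.0% for C2) rest on assumed prevalences and are not evidence that the reported values will be badly off.

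The interval fault is real, but its direction depends on the results. PPV intervals are about 1.5 times too wide at 80/70 if images are independent and the quotas are met. Correlation within phlebologist would reduce that excess and could remove it. NPV intervals under-cover at high sensitivity.

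Nothing here touches the primary analysis intervals or any study decision. Two named secondary measures would, however, be reported without the condition that makes them interpretable, so the text should be changed.

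**What to change.** In Section 1.6:

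1. Derive PPV and NPV by Bayes' formula from the estimated sensitivity and specificity at the source prevalences in Section 1.11 (C1 26%, 30.9%, 34.3%; C2 19%, 19.3%, 21.3%), labelled as general-population values. Add a stated range labelled as an assumption for clinic patients, for example C1 20-50% and C2 10-40%.
2. Use logit-scale intervals built from the variances of sensitivity and specificity with class totals fixed. Cluster those variances by phlebologist, or state that independence between images is assumed.
3. Label any raw a/(a+b) and d/(c+d) as 'at quota prevalence'.
4. State that specificity, LR+, LR- and the converted values still assume the quota's comparator mix. List false-positive counts by comparator group so that readers can reweight.

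The cost is a few lines of text, with no new data or patients. A short table replaces one number each. Dependence on the comparator mix remains and can only be stated. Even under independence, logit coverage for C2 NPV at Se 95% is about 93-94% with 372 analysed. In the other settings checked at that size (Se/Sp 80/70, 90/90, 95/90 and 95/95) it is 94.7-95.3% for both PPV and NPV.

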## 1.3 Descriptive statistics

Continuous (quantitative) data will be presented as number of valid observations, arithmetic mean, standard deviation, median, interquartile range (presented as 1st and 3rd quartiles), minimum and maximum.

Categorical (quantitative) data will be presented as number of valid observations, number of observations falling into each category (absolute frequency), relative frequency (presented as % values).

95% confidence intervals will be presented for all types of data to measure the precision of sample estimate. Confidence intervals will be based on t-distribution for quantitative data, and on the binomial distribution (exact Clopper-Pearson method or Agresti-Coull method) for qualitative data.

Concurrent conditions and adverse events will be classified using the current version (at the time of database lock) of MedDRA (Medical Dictionary for Regulatory Activities). Concomitant medications will be classified using the most up-to-date version (at the time of database lock) of ATC (anatomical, therapeutical and chemical) classification system.

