## 1.10 Significance level

Significance level alpha = 0.05 will be used for all two-sided tests. All confidence intervals will be 95% two-sided.

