- 1) Null hypothesis (not acceptable) levels of both sensitivity and specificity are set to 60% (0,6), i.e. such level of effectiveness of detecting signs of early stages of CVD will be too low for screening purposes
- 2) Expected (detectable) level of sensitivity and specificity:
  - a. Target (expected) sensitivity – 80% or higher
  - b. Target (expected) specificity – 70% or higher
- 3) Power of analysis is set to 80% (accordingly, type II error is equal to 0,20)
- 4) Significance level is set to 5% (accordingly, type I error is equal to 0,05)
- 5) Expected prevalence is set to 70% (0,70)
- 6) Exact binomial distribution approach and the Agresti-Coull approach will be used
- 7) Up to 10% of cases can be lost for statistical analysis (due to loss of absence of reliable data for both reference standard and test under study)

Calculations results:

For Se:

- exact binomial distribution approach: a total sample size is 90 pts, the amount of patients with C 1-2 is 45;
- Agresti-Coull approach: total sample size is 88 pts, the amount of patients with C 1-2 is 44.

For Sp:

- exact binomial distribution approach: a total sample size is 362 pts, the amount of patients with C 1-2 is 181;
- Agresti-Coull approach: a total sample size is 372 pts, the amount of patients with C 1-2 is 186.

In accordance with generally accepted approach, we must choose the largest estimation among the estimation for Se and Sp, so we chose the result for Sp, the total sample size estimation is 372, and the amount of patients with C 1-2 is 186.

Taking possible 10% loss of data (41 cases), a total of 413 patients (or more, 414 for example) should be enrolled in the study.

A half of them (207 patients) are patients with C1 or C2 class (namely, 3/5 of the patients with C1 ( $n= 124$ ) and 2/5 of the patients with C2 ( $n= 83$ )).

Another half of patients ( $n=207$ ) will include either persons without any signs of CDV (or with C0 class) or with C3-6 classes (namely, 4/5 of these patients are without CVD or with C0 ( $n= 166$ ), and 1/5 of the patients with C3-6 classes ( $n= 41$  cases)).

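### Section 1.6 gives LR+ and LR- a Wald interval with no scale or zero-cell rule; read literally, error is lopsided, slightly at planning values and materially for LR- if the app performs well

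*Combined protocol and SAP*

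**What the plan says.** Section 1.6 (Secondary endpoints) defines LR+ as sensitivity over 100 minus specificity and LR- as 100 minus sensitivity over specificity, separately for C1 and C2. One sentence then sets the interval for all four secondary measures: "95% confidence intervals will be calculated using the normal approximation (Wald's) method for PPV, NPV, LR+ and LR- parameters". Nothing is said about transformation, limits outside the possible range, or empty cells.

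Elsewhere the plan does not use Wald. Section 1.5 has "95% exact binomial confidence intervals calculated using the Clopper-Pearson or Agresti-Coull method will be calculated for both sensitivity and specificity", and section 1.3 bases intervals "on the binomial distribution (exact Clopper-Pearson method or Agresti-Coull method) for qualitative data". Section 1.10 adds "All confidence intervals will be 95% two-sided".

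The likelihood ratios are listed as secondary variables. The Aim of the program section also says, under the primary goal, that they will be calculated once sensitivity and specificity are known. The performance targets in section 1.11 have no ceiling: "Target (expected) sensitivity – 80% or higher", with a matching 70% floor for specificity.

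**The concern.** Each likelihood ratio is a ratio of two proportions from independent groups (reference-positive and reference-negative patients). Its estimate is right-skewed and cannot fall below zero. A symmetric natural-scale interval ignores both facts, so its two tails carry unequal error and its lower limit can be negative.

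The direction differs between the two ratios. For LR-, the typical miss is an upper limit that is too low, which overstates how well a negative app result rules out C1 or C2. For LR+, the typical miss is also an interval lying below the true value, but there it understates the app. What is at stake is whether the reported LR intervals have the 95% level that section 1.10 promises, above all LR- for C2, the class with fewer positives.

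**Working it through.** **Inputs.** Section 1.11 gives 372 evaluable patients, half with C1 or C2 (186), split 3:2; 124 C1 and 83 C2 are enrolled, with 10% loss allowed. Applying the loss evenly (an assumption): C1 positives 0.9 × 124 = 111.6, taken as 112, leaving 372 − 112 = 260 negatives; C2 positives 0.9 × 83 = 74.7, taken as 75, leaving 297. Planning values are Se 0.80 and Sp 0.70. Higher values are assumptions, shown as a range.

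**The plan's own figures.** The documents give no interval or coverage figure for the likelihood ratios. The sample size does reproduce: a two-sided 5% test with 80% power against 0.60 needs 45 (exact) or 44 (Agresti-Coull) for 0.80, and 181 or 186 for 0.70. Doubling gives 90, 88, 362 and 372, and 372/0.9 = 413.3, so 414.

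**Formulas** (delta method, natural scale; n1 positives, n0 negatives):

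- Var(LR+) = LR+² × [(1−Se)/(n1·Se) + Sp/(n0·(1−Sp))]
- Var(LR−) = Se(1−Se)/(n1·Sp²) + (1−Se)²(1−Sp)/(n0·Sp³)
- Literal Wald: LR ± 1.96·SE. Log scale: LR × exp(±1.96·SE/LR).

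**One example, C2, 3 of 75 missed and 285 of 297 true negatives.** 1−Se = 0.04, Sp = 0.9596, LR− = 0.0417. The variance is 0.000556 plus a negligible second term, so SE = 0.0236. Wald: 0.0417 ± 0.0463, that is −0.005 to 0.088. Log scale: SE/LR = 0.566, giving 0.014 to 0.126.

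**Coverage.** All pairs of true-positive and false-positive counts were enumerated as two independent binomials (no clustering by physician), and each literal Wald interval was checked against the true ratio. Entries are percentages; misses are shown as upper limit too low / lower limit too high.

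| Se/Sp | Class | LR+ coverage | LR+ misses | LR− coverage | LR− misses | LR− lower limit < 0 |
|---|---|---|---|---|---|---|
| 0.80/0.70 | C1 | 95.0 | 4.0 / 1.0 | 94.2 | 4.3 / 1.5 | 0 |
| 0.80/0.70 | C2 | 95.1 | 3.6 / 1.3 | 93.8 | 4.8 / 1.4 | 0.01 |
| 0.90/0.90 | C1 | 94.9 | 5.0 / 0.03 | 92.9 | 6.0 / 1.1 | 0.3 |
| 0.90/0.90 | C2 | 94.8 | 5.1 / 0.1 | 94.0 | 5.1 / 0.8 | 5.0 |
| 0.95/0.95 | C1 | 93.9 | 6.1 / 0.0 | 91.7 | 7.7 / 0.6 | 18 |
| 0.95/0.95 | C2 | 94.0 | 6.0 / 0.0 | 89.0 | 10.6 / 0.4 | 46 |

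**Zero false negatives.** Then 1−Se is estimated as 0, both terms of Var(LR−) vanish, and the interval is 0 to 0. For C2 the chance is 0.95^75 = 2.1% at Se 0.95 and 0.98^75 = 22% at Se 0.98. At 0.98/0.98, C2 LR− coverage is 77.9%.

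**Alternatives, same enumeration.** The Miettinen-Nurminen score interval covers 94.5 to 95.3% for both ratios and both classes at 0.80/0.70, at 0.95/0.95 and at Se 0.95 with Sp 0.97. The log-scale interval covers 95.1 to 95.2% at 0.80/0.70 and 95.2 to 97.0% at 0.95/0.95, but cannot be computed for LR− when there are no false negatives.

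**The case against.** **The scale is not stated.** A normal approximation on log(LR), back-transformed, is also a Wald interval. Under that reading negative limits cannot occur and coverage at the planning values is nominal. This stands as a caution: the defect is certain only for the literal reading. That reading is the more natural one, because PPV and NPV share the sentence, and the log reading would still need a zero-cell rule that the plan lacks.

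**At the planning values little changes.** For C2 at its expected counts, LR− is 0.155 to 0.417 (Wald) against 0.181 to 0.452 (log), and LR+ is 2.11 to 3.22 against 2.17 to 3.28. No reader would conclude differently. This stands.

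**The large effects rest on assumed performance.** Accuracies of 0.95 appear nowhere in the documents; the targets merely permit them. Part of the C2 shortfall is also binomial discreteness: at 0.90/0.90, LR− coverage is 94.0% with 75/297 but 91.9 to 93.6% at the other class sizes tried (124/290, 112/260, 83/331 and 74/298). This stands too.

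**No decision hangs on these intervals.** There is no LR threshold or hypothesis, and section 1.15 allows documented changes of method. That limits the consequence but is no reason to keep the sentence.

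A reader might infer that the likelihood ratios are the only summaries free of the quota-fixed case mix, so that the study's usable result is compromised. The documents do not support this: sensitivity and specificity are equally free of class prevalence, are primary, and have binomial intervals under section 1.5.

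**Conclusion.** The point holds as an avoidable weakness in secondary intervals. Followed literally, section 1.6 gives LR intervals with unbalanced error. At Se 80% and Sp 70% the cost is about one percentage point of LR- coverage, with LR+ coverage nominal and its misses mostly against the app. At an assumed 95%/95%, LR- coverage is 91.7% (C1) and 89.0% (C2), and the upper limit is too low in 7.7% and 10.6% of samples against a nominal 2.5%.

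Two stronger readings are tempting and should not be drawn. One is that the plan's LR intervals are badly wrong whatever the app's performance; the planning-value results show otherwise. The other is that the method systematically flatters the app; that is true of LR- only.

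The figures rest on the natural-scale reading, even 10% loss across classes and simple binomial sampling. The primary sensitivity and specificity intervals and the sample size of 414 do not change.

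**What to change.** In section 1.6, remove LR+ and LR- from the Wald sentence and add: *95% two-sided intervals for LR+ and LR- will be computed as for a ratio of two independent proportions by the asymptotic score method (Koopman / Miettinen-Nurminen).* At minimum, state that they are computed on the log scale, with a named correction (for example adding 0.5) when a cell is zero. The log option is adequate rather than ideal: with the 0.5 correction, C2 LR- misses at 0.95/0.95 are still one-sided (0.0% and 3.4%), and coverage at 0.98/0.98 is 93.6%.

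The cost is one sentence and standard code, with no new data and no change to design or sample size. The intervals become asymmetric, and a well-performing app will show a higher upper LR- limit: 0.126 instead of 0.088 in the worked example on the log scale. The choice should be recorded before the app's results are compared with the reference diagnoses.
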